6.2.2 Phone Visits 4 and 5 (Titration Period Study Days 4 and 8)

Site personnel will contact the subject via telephone on Titration Period Study Days 4 and 8 and record the following:

- AEs
- AESI
- Concomitant medications

In addition, site personnel will review study medication dosing procedure and the diary entries with the parent/caregiver.

6.2.3 Clinic Visit 6 (Titration Period Study Day 15)

Subjects will report to the clinic in the morning on Titration Period Study Day 15. Subjects should not take their morning dose(s) of AED medication prior to reporting to the clinic. The following procedures will be performed:

- Review current seizure activity (number/type/duration) from diary since previous visit
- Record concomitant medications
- Abbreviated physical examination, including height and weight, and calculation of BMI
- Abbreviated neurological examination
- Obtain vital signs
- Urine pregnancy test for females of child-bearing potential
- Laboratory evaluation (serum chemistry and hematology, and urinalysis)
- Urine THC panel
- Whole blood CBD

Confidential Page 55 of 182

- Collect plasma sample for AED pharmacokinetic evaluation prior to the morning dose of study medication(s)
- Collect and review diary with parent/caregiver
- Dispense diary
- C-SSRS Children's Since Last Visit Assessment (Appendix 2)
- Clinical Global Impression Improvement (assessed by parent/caregiver)
- Clinical Global Impression Improvement (assessed by investigator)
- Record AEs
- Record AESI
- Collect used, partially used and unused study medication; perform drug accountability and review with parent/caregiver
- Dispense study medication

6.2.4 Phone Visit 7 (Maintenance Period Study Day 29)

Site personnel will contact the subject via telephone on Maintenance Period Study Day 29 and record the following:

- AEs
- AESI
- Concomitant medications

In addition, site personnel will review the diary entries with the parent/caregiver.

6.2.5 Clinic Visit 8 (Maintenance Period Study Day 43)

- Subjects will report to the clinic in the morning on Maintenance Period Study Day 43. Subjects should not take their morning dose(s) of study medication and AED medication prior to reporting to the clinic. The following procedures will be performed:
- Review current seizure activity (number/type/duration) from diary since previous visit
- Record concomitant medications
- Abbreviated physical examination, including height and weight, and calculation of BMI (Note: if the subject's weight is ±25% of the weight at Study Day-1, the IMP dose will be recalculated)

Confidential Page 56 of 182

- Obtain vital signs
- Doppler ECHO (this must be obtained any time between Study Day 40 and Study Day 54)

 Urine pregnancy test for fame1
- Laboratory evaluation (serum chemistry and hematology, and urinalysis)
- Urine THC panel
- Whole blood CBD
- Collect plasma sample for ZX008 pharmacokinetic evaluation at the following timepoints: within 1 hour prior to the morning dose of study medication, and 1, 2 and 4-6 hours after the morning dose of study medication
- Collect plasma sample for AED pharmacokinetic evaluation prior to the morning dose of study medication(s)
- Collect and review diary with parent/caregiver
- Dispense diary
- C-SSRS Children's Since Last Visit Assessment (Appendix 2)
- BRIEF (Appendix 3
- OOLCE (Appendix 4
- PedsQL (Appendix 6)
- PedsQL Family Impact module (Appendix 6)
- Affective symptoms of parent/caregiver using the HADS scale (Appendix 8)
- Clinical Global Impression Improvement (assessed by parent/caregiver)
- Clinical Global Impression Improvement (assessed by investigator)
- Record AEs
- Record AESI
- Collect used, partially used and unused study medication; perform drug accountability and review with parent/caregiver
- Dispense study medication

Page 57 of 182 Confidential

6.2.6 Phone Visit 9 (Maintenance Period Study Day 57)

Jalikori Zalio Site personnel will contact the subject via telephone on Maintenance Period Study Day 57 and record the following:

- **AEs**
- **AESI**
- Concomitant medications

In addition, site personnel with review the diary entries with the parent/caregiver

6.2.7 Clinic Visit 10 (Maintenance Period Study Day 71

Subjects will report to the clinic on Maintenance Period Study Day 71. The following procedures will be performed:

- Review current seizure activity (number/type/duration) from diary since previous visit
- Record concomitant medications
- Abbreviated physical examination, including height and weight, and calculation of BMI
- Obtain vital signs
- Urine pregnancy test for females of child-bearing potential
- Laboratory evaluation (serum chemistry and hematology, and urinalysis)
- Urine THC panel
- Whole blood CBD
- Collect and review diary with parent/caregiver
- Dispense diary
- C-SSRS Children's Since Last Visit Assessment (Appendix 2)
- Clinical Global Impression Improvement (assessed by parent/caregiver)
- Clinical Global Impression Improvement (assessed by investigator)
- Record AEs
- Record AESI
- Collect used, partially used and unused study medication; perform drug accountability

Page 58 of 182 Confidential

and review with parent/caregiver

Dispense study medication

At Clinic Visit 10, compliant subjects who have tolerated IMP should be presented with the ICF for the open-label extension study. Informed consent for the open-label extension study must be signed at Visit 12 or earlier in order to enter the open-label extension study.

6.2.8 Phone Visit 11 (Maintenance Period Study Day 85)

Site personnel will contact the subject via telephone on Maintenance Period Study Day 85 and record the following:

- AEs
- AESI
- Concomitant Medications

In addition, site personnel with review the diary entries with the parent/caregiver.

6.2.9 Clinic Visit 12 (Maintenance Period Study Day 99): End of Study/Early Termination

The End-of-Study participation for an individual subject occurs after he/she has received IMP for 12 weeks in the Maintenance Period. At the End-of-Study visit, the subject may enroll into the separate extension study if they have completed 12 weeks of treatment in the Maintenance Period. Other circumstances for participation in the extension study are described in Section 4.8.

The End-of-Study visit may also occur if the subject withdraws participation from the study or the sponsor terminates the study. If the subject withdraws participation from the study, they may on a case-by-case basis, be eligible for entrance into the separate open-label extension study after consideration of the circumstances of the early termination and the potential benefit- risk of continued participation in a ZX008 trial. The decision whether to permit open-label extension study participation resides solely with the sponsor, who may consult with the site investigator. If the sponsor terminates the study early, the subject may or may not be offered enrollment into the open-label extension, depending on the reason for termination.

Subjects will visit the clinic for the End-of-Study visit if one the following events occur:

- The subject withdraws or is withdrawn from participation in the study.
- 2. The sponsor terminates the study.
- 3. The subject completes all study related visits and procedures.

The following procedures will be performed:

Confidential Page 59 of 182

- Review current seizure activity (number/type/duration) from diary since previous visit
- Record concomitant medications
- Complete physical examination, including height and weight, and calculation of BMI
- Complete neurological examination
- Obtain vital signs
- 12-lead electrocardiogram
- Doppler ECHO (must be performed any time between Study Day 90 and Study
- Day 113; if subject terminates early from the study, the ECHO should be scheduled as soon as practical). If the Study Day 43 ECHO was completed ≤30 days prior to early termination, the Visit 12 ECHO will not be performed provided the parent/guardian agrees to bring the subject to the clinic for the eardiac follow-up visit (see Table 7).
- Urine pregnancy test for females of child-bearing potential
- Laboratory evaluation (serum chemistry and hematology, and urinalysis)
- Urine THC panel
- Whole blood CBD
- Collect plasma sample for AED pharmacokinetic evaluation prior to the morning dose of study medication(s)
- Tanner Staging for subjects >7 years of age (Appendix 5)
- Collect and review diary with parent/caregiver
- Dispense diary
- C-SSRS Children's Since Last Visit Assessment (Appendix 2)
- Clinical Global Impression Improvement (assessed by parent/caregiver)
- Clinical Global Impression Improvement (assessed by investigator)
- BRIEF (Appendix 3)
- QOLCE (Appendix 4)
- PedsQL (Appendix 6)
- PedsQL Family Impact module (Appendix 6)

Confidential Page 60 of 182

- Parent/Caregiver QoL using the EQ-5D-5L scale (Appendix 7)
- Affective symptoms of parent/caregiver using the HADS scale (Appendix 8)
- Record AEs
- Record AESIs
- Collect used, partially used and unused study medication; perform drug accountability and review with parent/caregiver
- Dispense study medication

Informed consent for the open-label extension study must be signed at Visit 12 (if not signed earlier) in order to enter the open-label extension study.

6.3 POST-DOSE VISIT (CLINIC VISIT 13; STUDY DAY 113)

For subjects entering the open-label extension study, the subject will visit the clinic on Day 113. The following will be recorded/performed and the subject will immediately be enrolled in that separate study:

- Review current seizure activity (number/type/duration) from diary since previous visit
- AEs
- AESIs
- Concomitant medications
- Collect used, partially used and unused study medication; perform drug accountability and review with parent/caregiver

If the subject does not enter the open-label extension study (or discontinues from the study early), the subject will visit the clinic on Study Day 113 (or 14 days after the day of discontinuation). The following will be recorded/performed:

- Review current seizure activity (number/type/duration) from diary since previous visit
- AEs
- AESIs
- Concomitant medications
- Collect used, partially used and unused study medication; perform drug accountability and review with parent/caregiver

Confidential Page 61 of 182

6.4 CARDIAC FOLLOW-UP VISIT (CLINIC VISIT 14; STUDY DAY 197-281)

If the subject completes the study but does not enter the open-label extension study or discontinues from the study early, the subject will return to the clinic for follow-up cardiac testing (ECHO, ECG, and in some cases physical examination). The timing and frequency of exams are in Table 7. Subjects on blinded medication who are found to have been on placebo are not required to participate in follow-up testing once the blind is broken at the end of the study. As the ECHO and ECG will be administered in a separate clinic than the pediatric neurology clinic, an asymptomatic subject receiving a second follow-up ECHO and ECG does not require a physical examination.

Subjects with positive findings on ECHO, ECG and/or physical examination should continue to be followed until the finding is resolved or stable and unlikely to change, with reports submitted as AESI to the ZX008 safety database.

Table 7: Schedule of Post-Treatment Cardiac Follow-up

	Duration of Blinded ^a or Fenfluramine Treatment				
Parameter	Less than 2 weeks Cumulative	2 to 4 weeks	>4 and <13 weeks	>13 weeks	Have had any cardiac sign or symptom regardless of the time on study drug ^b
ЕСНО	No	Yes,	Yes,	Yes,	Yes,
		3 months post-	3 months post-	3 and 6 months	3 and 6 months post-
		treatment	treatment	post-treatment	treatment, and until
		X			resolved, or stable and
			XO		unlikely to change
ECG	No	Yes,	Yes,	Yes,	Yes,
		3 months post-	3 months post-	3 and 6 months	3 and 6 months post-
		treatment	treatment	post-treatment	treatment and until
		1000)		resolved, or stable and
	×	(0)			unlikely to change
Physical	No	Yes,	Yes,	Yes,	Yes,
examination		3 months post-	3 months post-	3 months post-	3 and 6 months post-
		treatment	treatment	treatment only	treatment, and until
	60.				resolved, or stable and
3 I C 1 1: . 1 : . 1 1		•		-1111	unlikely to change

^a If blind is broken at the end of the study and a subject revealed to have taken only placebo, no further testing is required.

6.5 ESTIMATED BLOOD VOLUME COLLECTION

The maximum total blood volume collected during the study for clinical laboratory testing, genotyping, and PK will be approximately 99.7 mL, as outlined in Table 8.

Confidential Page 62 of 182

b Positive sign or symptom includes any development of valve thickening or regurgitation ("trace" or greater in mitral, aortic; mild or greater in pulmonary, tricuspid), or sign or symptom indicative of potential pulmonary hypertension as adjudicated by the IPCAB.

Table 8: Estimated Blood Volume Collection*

	Baseline Period (study day)		Titration + Maintenance Period (study day)				
Assessment	Screening (Day -42 to -41)	Randomization Day -1	Day 15	Day 43	Day 71	Day 99	Total
Clinical Chemistry	4mL	4mL	4mL	4mL	4mL	4mL	24mL
LH, FSH, Estradiol, Testosterone, Prolactin		4mL		4mL	4mL	4mL	16mL
Genotyping	5 mL			• • • • • • • • • • • • • • • • • • •	USI, OF	5	5 mL
Hematology	2mL	2mL	2mL	2mL	2mL	2mL	12mL
IGF-1, GH		2.5mL	, , , , ,	2.5mL	2.5mL	2.5mL	10 mL
Coagulation		2.7 m L	SUR				2.7mL
Cannabidiol	2mL	2mL	2mL	2mL	2mL	2mL	12mL
ZX008 PK plasma		be and		4 x 2 mL			8 mL
AED plasma sample	anno	1 x 2 mL	1 x 2 mL	1 x 2 mL		1 x 2 mL	8 mL
Volume for flushing indwelling catheter	Colifor			4 x 0.5 mL			2 mL
Approximate total blood volume per subject	13mL	19.2mL	10mL	26.5mL	14.5mL	16.5mL	99.7 mL

FSH=follicle stimulating hormone; GH=growth hormone; IGF-1=insulin-like growth factor 1; LH-luteinizing hormone; PK=pharmacokinetics

Confidential Page 63 of 182

^{*}In concordance with The Seattle Children's Research Foundation Guidance (Appendix 9), blood

collection volumes for children weighing up to 15 kg will be:

- the maximum allowable volume of blood in one draw is 22-30 mL (2.5% of total blood volume)
- the maximum in a 30-day period is 44-60 mL.

On Day 43/Visit 8 the pharmacokinetic blood draw will be completed as the priority and the blood draw for chemistry and hematology will be skipped for those subjects who weigh less than 13.5 kg, unless medical concerns (for example, from previous tests or reported side effects) prioritize chemistry and/or hematology.

If blood collection is restricted due to volume or due to inability to draw adequate volume, collection should be prioritized as shown in Table 9:

Table 9: Priorities for Blood Sample Collections

	Assessment	2	Priority
ZX008 PK sample		(), X.	Priority 1
Clinical chemistry			Priority 2
Cannabidiol		-0	Priority 2
AED plasma sample	10	2 70,	Priority 2
LH, FSH, estradiol, testoste	rone, GH, prolactin	0, 0	Priority 3
Hematology		, ,0,	Priority 3
IGF-1	V), XO	20,	Priority 4
Genotyping	8 8		One time collection any time during or after
	` O X	O	screening
Coagulation	Sot		One time collection any time before PK day

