7.2.5 Laboratory Measurements

Laboratory safety parameters will be analyzed using standard validated methods.

The following parameters will be assessed by the laboratory as described in Table 1 and Table 8:

- Hematology: hemoglobin, hematocrit, erythrocytes, erythrocyte mean corpuscular volume, leukocytes, mean corpuscular hemoglobin, mean corpuscular hemoglobin concentration, neutrophils, lymphocytes, monocytes, eosinophils, basophils and platelets
- Blood Biochemistry: albumin (ALB), alkaline phosphatase (AP), alanine aminotransferase (ALT; SGPT), aspartate aminotransferase (AST; SGOT), bicarbonate, blood urea nitrogen (BUN), calcium (Ca), carbon dioxide (CO₂), chloride (Cl), creatinine, creatine kinase, gamma-glutamyl transferase (GGT), globulin, glucose, lactate dehydrogenase (LDH), phosphorus, potassium (K), sodium (Na), thyroid function (T3, T4, and thyroid stimulating hormone [TSH]), total bilirubin, direct bilirubin, total cholesterol, total protein, triglycerides, uric acid.
- Tests of growth and precocious puberty: Growth hormone (GH), insulin-like growth factor-1 (IGF-1, low sensitivity), prolactin, Luteinizing Hormone (LH), Follicle

Confidential Page 68 of 182

Stimulating Hormone (FSH), testosterone, estradiol

- Epilepsy genotype panel
- Coagulation: Prothrombin time (PT)/International normalized ratio (INR), activated partial thromboplastin time (PTT)
- Whole blood cannabidiol
- Urinalysis: analysis for pH, glucose, ketones, nitrite, protein, bilirubin, urobilinogen, leukocyte esterase, and occult blood. Microscopic analysis will be performed for blood, all cell types, and casts.
- Urine pregnancy test: Urine pregnancy testing will be performed in female subjects of childbearing potential.
- Urine THC panel
- The investigator will receive the laboratory report from the central laboratory. After reviewing the report and evaluating any results that are outside the normal range, the investigator must sign and date the laboratory report.

Tests resulting in abnormal laboratory values that have been classified by the investigator as abnormal, clinically significant should be repeated as soon as possible after receiving the laboratory report to rule out laboratory errors.

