APPENDIX 9 – MAXIMUM ALLOWABLE BLOOD DRAW VOLUMES

Maximum allowable blood draw volumes:

PATIENT'S	WEIGHT	TOTAL VOLUME	MAXIMUM mL IN ONE BLOOD DRAW	MAXIMUM mL IN A 30-DAY PERIOD
Kg	lbs	mL	2.5% of total blood vol	5% of total blood vol
1	2.2	100	2.5	5
2	4.4	200	5	/10
3	3.3	240	6	12
4	8.8	320	8	16
5	11	400	10	20
6	13.2	480	12	24
7	15.4	560	14	28
8	17.6	640	16	32
9	19.8	720	18	36
10	22	800	20	40
11 thru 15	24 thru 33	880-1200	22-30	44-60
16 thru 20	35 thru 44	1280-1600	32-40	64-80
21 thru 25	46 thru 55	1680-2000	42-50	64-100
26 thru 30	57 thru 66	2080-2400	52-60	104-120
31 thru 35	68 thru 77	2480-2800	62-70	124-140
36 thru 40	79 thru 88	2880-3200	72-80	144-160
41 thru 45	90 thru 99	3280-3600	82-90	164-180
46 thru 50	101 thru 110	3680-4000	92-100	184-200
51 thru 55	112 thru 12/1	4080-4400	102-110	204-220
56 thru 60	123 thru 132	4480-4800	112-120	224-240
61 thru 65	134 thru 143	4880-5200	122-130	244-260
66 thru 70	145 thru 154	5280-5600	132-140	264-280
71 thru 75	156 thru 165	5680-6000	142-150	284-300
76 thru 80	167 thru 176	6080-6400	152-160	304-360
81 thru 85	178 thru 187	6480-6800	162-170	324-340
86 thru 90	189 thru 198	6880-7200	172-180	344-360
91 thru 95	200 thru 209	7280-7600	182-190	364-380
96 thru 100	211 thru 220	7680-8000	192-200	384-400

Based on blood volume of:

7 to 2 kg 100 mL/kg (pre-term infant)
>2 kg 80 mL/kg (term infant - adult)

This information is similar to that used by the Committee on Clinical Investigations at Children's Hospital in Los Angeles, and at Baylor College of Medicine in Dallas, TX.

Adapted by [name]. August 2001 Children's Hospital and Regional Medical Center Laboratory Seattle, WA

Confidential Page 147 of 182

APPENDIX 10 – PROTOCOL AMENDMENT 1

Summary of Changes

Clarifications and changes were made to the protocol and include the following:

Sponsor name change

Added new section of transition for subjects who will enter the open-label extension study Removed the following clinical laboratory tests at Visits 1 and 6: LH, FSH, estradiol,

testosterone, GH, prolactin, and IGF-1

Clarified the maximum dose of ZX008 is 30 mg/day

Clarified the collection duration of prior and concomitant AEDs

Clarified data to be collected with the use of rescue medication

Moved the BRIEF-P description from the efficacy section to the safety section

Added new section of collection of data for AEs requiring hospitalization

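### The Table 8 footnote applies Appendix 9's 11–15 kg blood-draw limits to every child up to 15 kg, so its limits are too high below 11 kg

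*Protocol*

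**What the plan says.** Table 8 in protocol Section 6.5 sets out the planned blood volume at each visit. Its footnote, which claims agreement with the guidance reproduced in Appendix 9, opens with "collection volumes for children weighing up to 15 kg will be" and gives two limits. For a single draw it says "the maximum allowable volume of blood in one draw is 22-30 mL (2.5% of total blood volume", and for any 30-day period it gives 44–60 mL. No lower weight is attached to either figure.

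Appendix 9 tabulates limits by weight, at 2.5% of total blood volume per draw and 5% per 30 days. Above 2 kg it assumes "80 mL/kg (term infant - adult". The pair 22–30 mL and 44–60 mL stands in the 11–15 kg row only. Single-kilogram rows below it give 20 and 40 mL at 10 kg and 18 and 36 mL at 9 kg.

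Section 4.1 admits children from age 2. Neither it nor Sections 4.2 and 4.3 set a minimum weight.

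**The concern.** The footnote takes one row of a weight-based table and drops the row's lower bound. For a child under 11 kg, the figures a site reads in Section 6.5 are higher than those in the appendix they are said to follow. They are also higher than the percentage printed beside the per-draw figure. An error in this direction permits too much blood rather than too little. At stake is blood-volume safety in the smallest children. No efficacy estimate or test depends on it.

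**Working it through.** **Inputs.** From Appendix 9: 80 mL/kg, 2.5% per draw, 5% per 30 days. From Table 8: the tube volumes by visit.

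**Formulas.** Per-draw limit = weight × 80 × 0.025 = 2 mL/kg. 30-day limit = weight × 80 × 0.05 = 4 mL/kg.

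**Reproducing the footnote.** At 11 kg: 2 × 11 = 22 mL and 4 × 11 = 44 mL. At 15 kg: 2 × 15 = 30 mL and 4 × 15 = 60 mL. The footnote matches the 11–15 kg row exactly, so the figures are right for that row and only the weight label is wrong.

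**Reproducing Table 8.** The visit sums are 13, 19.2, 10, 26.5, 14.5 and 16.5 mL, total 99.7 mL, as printed. The table's arithmetic is not in question.

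**Below 11 kg, using the footnote's lowest figures (22 and 44 mL):**

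| Weight | Blood volume | Appendix 9 limits (draw / 30 days) | Footnote excess | 22 mL as % | 44 mL as % |
|---|---|---|---|---|---|
| 11 kg | 880 mL | 22 / 44 mL | 0 / 0 mL | 2.50% | 5.00% |
| 10 kg | 800 mL | 20 / 40 mL | 2 / 4 mL | 2.75% | 5.50% |
| 9 kg | 720 mL | 18 / 36 mL | 4 / 8 mL | 3.06% | 6.11% |

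At the top of the footnote's per-draw range, 30 mL is 30/800 = 3.75% at 10 kg and 30/720 = 4.17% at 9 kg.

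**Does a planned visit fall in the gap?** Day -1 has no PK series. Its tubes are chemistry 4, hormones 4, hematology 2, IGF-1/GH 2.5, coagulation 2.7, cannabidiol 2 and AED 2, which sum to 19.2 mL. This meets 2 mL/kg from 19.2/2 = 9.6 kg. At 9 kg it is 19.2 − 18 = 1.2 mL over Appendix 9, yet inside the footnote's 22 mL. Without coagulation the visit is 19.2 − 2.7 = 16.5 mL, which fits at 9 kg.

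**30-day totals for adjacent visits.** Days -1 and 15: 19.2 + 10 = 29.2 mL. Days 71 and 99: 14.5 + 16.5 = 31.0 mL. For Day 43, take the larger reading of its rule for children under 13.5 kg, in which only the 4 mL chemistry and 2 mL hematology tubes are dropped: 26.5 − 6 = 20.5 mL. Days 15 and 43 are then 30.5 mL, and Days 43 and 71 are 35.0 mL. All are within 36 mL at 9 kg. At 9 and 10 kg the wrong 30-day figure therefore changes no scheduled pair. It would matter only for repeat or unscheduled samples, where it overstates the room available by 4 mL at 10 kg and 8 mL at 9 kg.

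**The case against.** The best defence is that the footnote corrects itself. It names Appendix 9 and prints the percentage, and a range of 22–30 mL cannot be one child's limit, so a careful reader must go to the percentage or the appendix, and both give the right answer. The Day -1 excess also has a remedy in the protocol: Table 9 gives coagulation as "One time collection any time before PK day". And no weight distribution is stated, so no affected child is shown. All of this limits the size of the point. It does not make the footnote's millilitre figures right below 11 kg, and a site that trusts them has no prompt to move the coagulation tube.

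A reader might infer a larger fault on Day 43. There the protocol says "the blood draw for chemistry and hematology will be skipped for those subjects who weigh less than 13.5 kg". Table 9 ranks chemistry Priority 2 and IGF-1 Priority 4, and Section 6.5 says that when volume is restricted "collection should be prioritized as shown in Table 9". The rule then seems to drop the more important tube and keep the less important one. The documents do not support calling that an error, for two reasons.

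- It is unclear which tubes the rule covers. Section 7.2.5 lists a separate group, "Tests of growth and precocious puberty: Growth hormone (GH), insulin-like growth factor-1 (IGF-1, low sensitivity), prolactin" among its members, and Tables 8 and 9 separate the tubes as well. But the Visit 8 instructions in Section 6.2.5 and the laboratory row of Table 1 have no separate line for hormones, IGF-1 or GH, while cannabidiol, PK and AED samples each have their own. If the skip covers the whole laboratory evaluation, Day 43 falls to 26.5 − (4 + 4 + 2 + 2.5) = 14.0 mL, which fits from 7 kg.
- Even on the narrow reading, a specific rule for one visit may depart from a general fallback order. It carries an override, "unless medical concerns (for example, from previous tests or reported side effects) prioritize chemistry and/or hematology", and chemistry is drawn on Days 15, 71 and 99. Keeping the hormones may be deliberate, since they are not drawn on Day 15. Reordering would give up Day 43 IGF-1/GH under 13.5 kg and, under 11 kg, Day 43 prolactin, whose elevation is an adverse event of special interest. That is a trade-off and not a correction.

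For the same reason, the 20.5 mL Day 43 total is not offered as a breach at 10 kg. The 0.5 mL excess needs the narrow reading, a visit total including 2 mL of flush counted as one draw, and Table 9 left unapplied.

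**Conclusion.** The footnote is wrong as written for children under 11 kg. Its lowest per-draw figure is 2 mL too high at 10 kg and 4 mL too high at 9 kg; its lowest 30-day figure is 4 mL and 8 mL too high. The one planned visit used here to show the effect is Day -1, which is 1.2 mL over at 9 kg and within limits from 9.6 kg. This rests on Appendix 9 being the intended standard, as the footnote says, and on treating Day -1 as a single draw. How many children under 11 kg would enrol is not stated, so practical exposure is unknown and may be small. Severity is minor, and efficacy is unaffected. On Day 43, the most the text supports is a request to clarify which tubes the rule covers.

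**What to change.** In the Table 8 footnote, limit 22–30 mL per draw and 44–60 mL per 30 days to children of 11–15 kg. Add that below 11 kg the Appendix 9 row for the child's weight applies, that is 2 mL/kg per draw and 4 mL/kg per 30 days (20 and 40 mL at 10 kg, 18 and 36 mL at 9 kg). Carry the same wording into the laboratory manual.

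The cost is a text change with no added procedure. From 9 kg to just under 9.6 kg, coagulation has to move off Day -1, which Table 9 already permits. Placing it at screening keeps it before dosing and brings that visit to 13 + 2.7 = 15.7 mL, inside the 18 mL limit at 9 kg.

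If Section 6.5 is being edited anyway, one clause saying whether the Day 43 skip includes the hormone and IGF-1/GH tubes would remove the ambiguity. No change to the Day 43 order is asked for.
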